#### **4.3.1.3.2. Supplementary Analyses**

Similar to the co-primary supplementary analyses, the methods specified in Section 4.2.3.3.1 will be applied to the selected key secondary binary endpoints using Treatment Policy Estimands (Section 4.3.1.2.2).

#### **4.3.1.3.3. Subgroup Analyses**

To evaluate the consistency of the efficacy, subgroup analyses of the following selected key secondary endpoints based on demographics, baseline disease characteristics and previous psoriasis medications and therapies will be performed (Section 4.6.6).

- IGA score of 0 at Week 16
- PASI 75 at Week 16
- PASI 100 at Week 16

### **4.3.2. Other Secondary Endpoints Analyses**

#### **4.3.2.1. Definition of Endpoints**

##### **4.3.2.1.1. Investigator's Global Assessment**

Refer to section 4.2.1.2 for details.

##### **4.3.2.1.2. Psoriasis Area and Severity Index**

Refer to section 4.2.1.1 for details.

##### **4.3.2.1.3. Dermatology Life Quality Index/Children's Dermatology Life Quality Index Score**

The Dermatology Life Quality Index (DLQI) is a dermatology-specific quality of life instrument designed to assess the impact of the disease on a participant's quality of life. It is a 10-item

questionnaire that in addition to evaluating overall quality of life, can be used to assess 6 different aspects that may affect quality of life: symptoms and feelings, daily activities, leisure, work or school performance, personal relationships, and treatment.

The DLQI is calculated by summing the score of each question resulting in a maximum of 30 and a minimum of 0. The higher the score, the more quality of life is impaired. A higher score indicates more severe disease. A score of  $\leq 1$  indicates no effect at all of disease on participant's health related quality of life, and an improvement of 5 points or more in total DLQI score is considered clinically meaningful improvement.

For a partially answered questionnaire (e.g., not all ten questions in a questionnaire were available):

- If one question's answer is not available (missing), this question will be scored missing. The total score will then be calculated.
- If two or more questions' answers are not available (missing), then the questionnaire is not scored. Hence, the total score will be set to missing.
- If one question from one of the 6 component scores is missing, the affected component score will be set to be missing.

The Children's Dermatology Life Quality Index (CDLQI) is a dermatology-specific quality of life instrument designed to assess the impact of the disease on a child's quality of life. It is an adapted version of DLQI. The CDLQI, a 10-item questionnaire has 4 items response options and a recall period of 1 week. In addition to evaluating overall quality of life, the CDLQI can be used to assess 6 different aspects that may affect quality of life: symptoms and feelings, leisure, school or holidays, personal relationships, sleep, and treatment.

The CDLQI is calculated by summing the score of each question resulting in a maximum of 30 and a minimum of 0. The higher the score, the more quality of life is impaired. For a partially answered questionnaire (e.g., not all ten questions in a questionnaire were available):

- If one question's answer is not available (missing), this question will be scored missing. The total score will then be calculated.
- If two or more questions' answers are not available (missing), then the questionnaire is not scored. Hence, the total score will be set to missing.
- If one question from one of the 6 component scores is missing, the affected component score will be set to be missing.
- If both questions in question 7 are completed, the higher of the two scores should be counted for question 7.

Meeting DLQI/CDLQI 0 or 1 criteria: defined as having a DLQI/CDLQI score of 0 or 1 with baseline DLQI/CDLQI score  $>1$ .

#### 4.3.2.1.4. Psoriasis Symptom and Sign Diary

Refer to section 4.3.1.1.3 for details.

Meeting PSSD sign score of 0 criteria: defined as having a PSSD sign score of 0 indicates absence of psoriasis signs.

#### 4.3.2.1.5. Body Surface Area (BSA)

Body surface area is a commonly used measure of involvement of skin disease. It is defined as the percentage of surface area of the body involved with the condition being assessed, (i.e., plaque psoriasis). The handprint method for assessing BSA will be used in this study, where the surface area of the participant's hand including the palm and all 5 digits is used as a guide to estimate 1% BSA.

#### 4.3.2.1.6. Static Physician's Global Assessment of Genitalia

The sPGA-G is a 6-point scale to assess the severity of genital psoriasis at a given time point (Merola 2017). The sPGA-G evaluates erythema, plaque elevation, and scale of genital psoriatic lesions. The severity of genital psoriasis is assessed as clear (0), minimal (1), mild (2), moderate (3), severe (4), and very severe (5). sPGA-G data is collected only for participants with active genital psoriasis at Week 0.

Meeting sPGA-G 0 or 1 criteria: having an sPGA-G score of clear (0) or minimal (1) and a  $\geq 2$ -grade improvement from baseline.

#### 4.3.2.1.7. Modified Nail Psoriasis Severity Index

The mNAPSI is an index used for assessing and grading the severity of nail psoriasis. Each of the participant's ten fingernails are evaluated on 7 features. The first three features are each scored from 0 to 3 in severity and are (1) onycholysis and oil-drop dyschromia, (2) pitting, and (3) nail plate crumbling. The next four features are each scored 0 absent or 1 present, and are (1) leukonychia, (2) splinter hemorrhages, (3) nail bed hyperkeratosis, and (4) red spots in the lunula. The score ranges from 0-13 per nail, and 0-130 for all fingernails.

#### 4.3.2.1.8. Patient-Reported Outcomes Measurement Information System-29 v2.1 (PROMIS-29)

The PROMIS-29 will be utilized in the adult population and is a 29-item generic HRQoL survey, assessing each of the 7 PROMIS domains (depression, anxiety, physical function, pain interference, fatigue, sleep disturbance, and ability to participate in social roles and activities) with 4 questions for each domain. The questions are ranked on a 5-point Likert Scale. There is also one 11-point rating scale for pain intensity.

The total raw score will be converted into a T-score for each participant based on the table in Appendix 6.9. The T-score rescales the raw score into a standardized score with a mean of 50 and an SD of 10. The standardized T-score is reported as the final score for each participant. Pain Intensity is presented as raw responses (0-10). For PROMIS domains of Depression, Anxiety, Physical Function, Pain Interference, Fatigue, a score of 50 is the average for the United States

general population with a standard deviation of 10, because testing was performed on a large sample of the general population. However, the other two domains (Ability to Participate in Social Roles and Activities and Sleep Disturbance) were not centered in a national sample. For these two domains, a score of 50 represents the average of the calibration sample which was generally more enriched for chronic illness, and a score of 50 likely represents somewhat sicker people than the general population. A higher PROMIS T-score represents more of the concept being measured. For negatively-worded concepts like Anxiety, a T-score of 60 is one SD worse than average. By comparison, an Anxiety T-score of 40 is one SD better than average. However, for positively-worded concepts like Physical Function, a T-score of 60 is better than average while a T-score of 40 is better. The physical component score (PCS) and mental component score (MCS) will be derived from the domain scores. Change from baseline in PROMIS-29 domain score is defined as the domain score minus the participant's baseline domain score, where a negative change indicates an improvement for the following domains:

- Anxiety
- Depression
- Fatigue
- Sleep disturbance
- Pain interference

and a positive change indicates an improvement for the following domains:

- Physical function
- Ability to participate in social roles and activities
- Physical health component score
- Mental health component score

#### **4.3.2.1.9. Patient-Reported Outcomes Measurement Information System-25 v2.0 (PROMIS-25)**

The PROMIS-25 will be utilized in the adolescent population and is a 25-item generic HRQoL survey utilized in the adolescent population. Six PROMIS domains (physical function mobility, anxiety, depressive symptoms, fatigue, peer relationships, pain interference) are assessed with 4 items, ranked on a 5-point Likert Scale. There is also one 11-point rating scale for pain intensity. The instrument is designed for use in ages 8-17 years of age and can be self-administered.

The total raw score will be converted into a T-score for each participant based on the table in Appendix 6.10. The T-score rescales the raw score into a standardized score with a mean of 50 and an SD of 10. Change from baseline in PROMIS-25 domain score: defined as the domain score minus the participant's baseline domain score, where a negative change indicates an improvement for the following domains:

- Anxiety
- Depressive symptoms
- Fatigue
- Pain interference

and a positive change indicates an improvement for the following domains:

- Physical function mobility
- Peer relationships

#### 4.3.2.1.10. Fingernail Physician's Global Assessment

The f-PGA is used to evaluate the current status of a participant's fingernail psoriasis on a scale of 0 to 4: clear (0), minimal (1), mild (2), moderate (3), and severe (4).

Meeting f-PGA 0 or 1 criteria: defined as having an f-PGA score of clear (0) or minimal (1).

#### 4.3.2.1.11. Physician's Global Assessment of Hands and/or Feet

The severity of hand and foot psoriasis has been assessed in various clinical studies using an hf-PGA instrument. The plaques are scored on a 5-point scale as: clear (0), almost clear (1), mild (2), moderate (3), and severe (4).

Meeting hf-PGA 0 or 1 criteria: defined as having an hf-PGA score of clear (0) or almost clear (1) and a  $\geq 2$ - grade improvement from baseline.

#### 4.3.2.1.12. Genital Psoriasis Sexual Frequency Questionnaire

The GenPs-SFQ will be utilized in the adult population and is a 2-item participant-reported instrument used to assess the impact of genital psoriasis on the frequency of sexual activity in the last 7 days. Item 1 assesses overall frequency of sexual activity in the last 7 days (none/zero, once, or 2 or more times), and item 2 assesses how frequently genital psoriasis symptoms have limited the frequency of sexual activity in the last 7 days (never [0], rarely [1], sometimes [2], often [3], or always [4]).

GenPs-SFQ data is collected only for adult participants with active genital psoriasis at Week 0.

Meeting GenPs-SFQ item 2 score 0 or 1 criteria: defined as having an GenPs-SFQ item 2 score of 0 or 1.

### 4.3.2.2. Estimands

#### 4.3.2.2.1. Estimands for Other Secondary Endpoints - at Week 16

The estimands for other secondary endpoints at Week 16 have the same attributes as the co-primary estimands in treatment and ICEs. The attributes for variable, population and population level summary for the other secondary endpoints are listed in [Table 5](#).

**Table 5: List of Variables, Populations and Population Level Summary for Other Secondary Endpoints**

Variable	Population	Population Level Summary
Change from baseline in BSA at Week 16	Same population as the primary estimand	Difference in treatment means
Change from baseline in PASI at Week 16		
Percent change in PASI at Week 16		
Change from baseline in PSSD symptom score at Week 16		
Change from baseline in PSSD sign score at Week 16		

**Table 5: List of Variables, Populations and Population Level Summary for Other Secondary Endpoints**

Change from baseline in DLQI total score at Week 16		
Percent change from baseline in mNAPSI score at Week 16	Patients $\geq 12$ years of age with moderate to severe plaque psoriasis and with a baseline mNAPSI score $>0$	
Change from baseline in each of the 8 individual domain score, PCS and MCS score of PROMIS-29 at Week 16	Adult patients with moderate to severe plaque psoriasis	
Change from baseline in CDLQI at Week 16	Adolescent patients with moderate to severe plaque psoriasis	
Change from baseline in each of the 7 individual domain score, and total score of the PROMIS-25 at Week 16	Adolescent patients with moderate to severe plaque psoriasis	
sPGA-G score of 0 or 1 and a $\geq 2$ -grade improvement from baseline at Week 16	Patients $\geq 12$ years of age with moderate to severe plaque psoriasis and with a baseline sPGA-G score $\geq 2$	Difference in treatment proportions
hf-PGA score of 0 or 1 and a $\geq 2$ -grade improvement from baseline at Week 16	Patients $\geq 12$ years of age with moderate to severe plaque psoriasis and with a baseline hf-PGA score $\geq 2$	
f-PGA score of 0 or 1 at Week 16	Patients $\geq 12$ years of age with moderate to severe plaque psoriasis and with a baseline f-PGA score $\geq 2$	
PSSD sign score of 0 at Week 16	Patients $\geq 12$ years of age with moderate to severe plaque psoriasis and with a baseline PSSD sign score $>0$	
GenPs-SFQ Item 2 score of 0 or 1 at Week 16	Adult patients with moderate to severe plaque psoriasis, with a baseline GenPs-SFQ item 2 score $\geq 2$ , and a baseline sPGA-G score $\geq 3$	
DLQI score of 0 or 1 at Week 16	Adult patients with moderate to severe plaque psoriasis and with a baseline DLQI Score $>1$	
CDLQI score of 0 or 1 at Week 16	Adolescent patients with moderate to severe plaque psoriasis and with a baseline CDLQI Score $>1$	

Note: composite strategy will be applied for patients with ICEs 1-2 and non-responders will be considered for binary endpoints and zero change / zero percent change will be considered for continuous endpoints.

#### 4.3.2.2.2. Estimands for Other Secondary Endpoints at Week 52 for adults

**Treatment and ICEs:** Same as those specified for the main estimand for key secondary endpoints at Week 52 (Section 4.3.1.2.1)

**Variable and Population:** The variable, population and summary measure for the other secondary binary endpoints are listed in Table 6 below.

**Table 6: List of Variable, Population, and Population Level Summary for Other Secondary Endpoints at Week 52 in Adults**

Variable	Population	Population Level Summary
IGA score of 0 or 1 and a $\geq 2$ -grade improvement from baseline at Week 52	Adult patients with moderate to severe plaque psoriasis, who are IGA 0 or 1 responders randomized at Week 24.	difference in proportions
IGA score of 0 at Week 52	Adult patients with moderate to severe plaque psoriasis, who are IGA 0 responders randomized at Week 24.	
PASI 100 at Week 52	Adult patients with moderate to severe plaque psoriasis, who are PASI 100 responders randomized at Week 24.	
Time to loss of IGA 0 or 1 response	Adult patients with moderate to severe plaque psoriasis, who are IGA 0 or 1 responders randomized at Week 24.	hazard ratio

**4.3.2.2.3. Estimands for Other Secondary Endpoints at Week 52 in Adolescents****Treatment:** JNJ-77242113**Population:** Adolescent patients with moderate to severe plaque psoriasis**Intercurrent event:** The ICEs and corresponding strategies are same as those defined in co-primary estimands.**Variable and Population Level Summary:** The variable and summary for the other secondary binary endpoints at Week 52 are listed in the below [Table 7](#).**Table 7: List of Variable and Population Level Summary for Other Secondary Endpoints at Week 52 in Adolescents**

Variable	Population Level Summary
IGA score of 0 or 1 and a $\geq 2$ -grade improvement from baseline at Week 52	proportions
PASI 75 at Week 52	
PASI 90 at Week 52	

**4.3.2.3. Analysis Methods**

The other secondary endpoints will be analyzed using the estimands described in section [4.3.2.2](#) for FAS or randomized at Week 24 analysis set. All statistical testing will be performed at the 2-sided 0.05 significance level. No adjustments for multiple comparisons will be made for other secondary endpoints. Nominal p-values for other secondary and exploratory endpoints will be reported but should not be used to infer statistical significance.

**Binary Endpoints**

The same strategies for addressing ICEs for key secondary analyses (binary endpoints) will be used for other secondary binary endpoints. The proportions of participants achieving a clinical

response for the efficacy endpoints will be provided by intervention group. The p-values, difference in proportions and 95% CIs will be provided based on the same model for key secondary endpoints specified in Section 4.3.1.3.1.

In addition, PSSD sign score of 0 at Week 16 will be compared between treatment group, among adolescent participants with a baseline PSSD sign score > 0, using a CMH test stratified by geographic region.

### **Continuous Endpoints**

The analysis strategies for ICEs:

- Participants experiencing ICEs 1, 2 and 4 (only apply to Week 52 endpoints after retreatment among adult participants) will be handled with composite strategy and data will be imputed with a zero change (or zero improvement) from baseline from that point onward.
- Participants experiencing ICE 3 will be handled by the treatment policy strategy and observed data will be used regardless of intercurrent events. For participants experiencing multiple ICEs, ICEs 2 and 4 will override an ICE 3.
- Missing data will not be imputed after applying the rules for ICEs. Missing data will be accounted for through correlation of repeated measures in the MMRM model.

For repeated measure continuous endpoints, treatment comparisons will be performed using a MMRM model. The MMRM will include treatment, age group, baseline weight, geographic region and baseline value, as explanatory factors, if applicable. The MMRM model will also include visit, treatment group by visit, and baseline value by visit interaction as additional explanatory factors. An unrestricted (UN) variance-covariance matrix for repeated measures within a participant will be used. If the model with unstructured covariance structure does not converge, alternative covariance structures will be tried in the following order, with the first structure that converges being used in the analysis: heterogeneous Toeplitz, standard Toeplitz, and autoregressive of order 1. The LS mean estimates and their corresponding 95% CI will be provided at each timepoint. In addition, the estimates of LS mean difference and 95% CIs between treatment groups will be provided.

Analysis of covariance will be used to analyze some continuous endpoints when appropriate. The ANCOVA will include treatment group, baseline value, baseline weight, geographic region and age group. The LS mean estimates and their corresponding 95% CI will be provided. In addition, LS mean difference and 95% CIs between treatment groups will be provided.

The analysis of time to loss of IGA 0 or 1 response will be performed in the same manner as the key secondary analyses of time to loss of PASI responses (refer to section 4.3.1.2.1) with the same data handling rule for ICEs and missing data.

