Clinical Pharmacology Assessments																
JNJ-77242113 concentration (plasma) ^c		X		X		X	X			X		X		X		Collect 1 trough and 1 peak sample at W4 and W16. Details to be specified during training. If peak/trough collection at the W4 and W16 visits is not feasible, collection at an alternative visit is allowed.

Period	Screen-ing	Placebo-controlled					JNJ-77242113 Treatment		Randomized withdrawal and retreatment						Unscheduled ^{a,b}	Notes: See Section 1.3.2 for Early Termination Visit procedures.
Week (W)	-5-0	0	2	4	8	12	16	20	24	28	32	36	44	52		
Visit Window (days)			±2	±2	±4	±4	±4	±4	±4	±4	±4	±4	±4	±4		
Study Procedure																
Antibodies to JNJ-77242113 (serum)		X		X		X	X			X		X		X		
Pharmacodynamics and Biomarkers																
Serum Biomarkers	X	X		X			X		X	X		X		X		Sample collection and testing will comply with local regulations.
Skin biopsy (optional skin biomarker substudy)		X							X					X		W0: Collect 1 lesional and 1 nonlesional biopsy. W24 and W52: Collect 1 lesional biopsy. Sample collection and testing will comply with local regulations.
Pharmacogenomics (DNA)																
Whole blood sample collection (optional substudy)		X														May be collected after W0 without constituting a protocol deviation. Sample collection and testing will comply with local regulations.
Ongoing Participant Review																
Concomitant therapy	X	X	X	X	X	X	X	X	X	X	X	X	X	X	X	Record all medications taken and new or worsening AEs reported after signing the ICF.
Adverse events	X	X	X	X	X	X	X	X	X	X	X	X	X	X	X	

- Additional assessments may be performed at the Unscheduled Visit at the investigator's discretion.
- During the randomized withdrawal and retreatment period (Week 24 to Week 52) if a participant's psoriasis worsens and the participant and investigator would like to have the participant return to the site for reevaluation of PASI score an Unscheduled Visit can be conducted. At this visit if the participant is part of the blinded treatment group withdrawn from JNJ-77242113 treatment and has lost 50% or greater of their PASI score from Week 24, the participant will be retreated with JNJ-77242113 in a blinded manner. If a participant is not part of the withdrawn treatment group, they will continue on their treatment per study design.

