The proportions of participants achieving a key secondary efficacy response will be summarized and compared between treatment groups in the same manner as the co-primary endpoints using the appropriate stratification factors. Similar data handling rules as the primary endpoints will be used for the key secondary binary endpoints. Specifically, composite strategy will be used for ICE 1-2 (as defined in Section 9.3.2) and/or ICE 4 (meeting retreatment criterion during the randomized withdrawal period; only applicable to Week 52 endpoints) where participants with those ICEs are considered as non-responders; treatment policy strategy will be used for ICE 3 (Section 9.3.2) where observed data will be used. After application of ICEs, participants with missing data will be imputed as non-responders. The same statistical method as that for the co-primary endpoints using the appropriate stratification factors will be used for analyzing the binary endpoints using the appropriate stratification factors (ie, age group, baseline weight category for adults, and geographic region for endpoints during the placebo-controlled period and geographic regions and PASI 90 response status at Week 24 for Week 52 endpoints) (Section 9.3.2). The analyses related to the time to event endpoints during the randomized withdrawal period will be performed using log-rank test stratified by geographic region and PASI 90 response status at Week 24.

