**ICEs and their corresponding strategies:**

Same ICEs 1-3 as those defined in the co-primary estimands. In addition, ICE 4 is defined as meeting criteria of loss of  $\geq 50\%$  Week 24 PASI improvement. Patients with this ICE will be handled using the composite strategy.

**Variable, Population and Population Level Summary:** Refer to [Table 4](#)

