##### **Binary Endpoint Analyses**

The binary key secondary endpoints will be analyzed using the main estimands described in section 4.3.1.2.1. Composite strategy will be used for ICEs 1, 2 and/or 4 (as applicable) where participants with those ICEs will be considered as non-responders and treatment policy strategy will be used for ICE 3 where observed data will be used. For the analysis at Week 52, participants experiencing an ICE 2 from Week 24 to Week 52 will be considered non-responders at Week 52, regardless of whether an ICE 2 occurred prior to Week 24. After the application of ICEs, participants with missing data will be imputed as non-responders. The proportions of participants achieving a key secondary efficacy response will be summarized and compared between treatment groups in the same manner as the co-primary endpoints using the appropriate stratification factors. For endpoints at or prior to Week 16, the stratification factors for randomization at baseline may be used in analyses. Geographic region may be removed as a stratification factor in CMH tests for endpoints with low response rates. For the analyses of PASI 75 at Week 52, stratification factors of PASI 90 response status at Week 24, and geographic region may be used in the analyses. A stratification factor of geographic region may be used for the analysis of PASI 90 at Week 52.

In addition, key endpoints at or prior to Week 16 (defined in 4.3.1.2.1) will be summarized and compared between treatment group among adolescent participants using a CMH test stratified by geographic region.

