#### **4.4.2.2. Analyses From Week 24 Through Week 52 – Randomized Withdrawal and Retreatment Period**

##### **Randomized Withdrawal Period**

To evaluate the maintenance of efficacy of JNJ-77242113 compared with treatment withdrawal

during the randomized withdrawal period, efficacy analyses at Week 52 and from Week 24 through Week 52 (withdrawal and retreatment period) will be summarized among adult participants who were rerandomized at Week 24.

- **Placebo (withdrawal group):** participants rerandomized to the placebo group at Week 24
- **JNJ-77242113:** participants rerandomized to the JNJ-77242113 treatment group at Week 24

Participants experiencing ICEs 1, 2 and/or 4 between Week 24 and Week 52 will be handled in the same manner as the other secondary analyses (section 4.3.2.3).

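### For continuous endpoints the SAP applies ICE 4 only after retreatment, which conflicts with its own definition of ICE 4 and, read literally, scores the same relapse differently in the two re-randomized arms (minor)

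*SAP*

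**What the plan says.** **Definition.** SAP 4.3.1.2.1, for the Week 52 key secondary endpoints: "In addition, ICE 4 is defined as meeting criteria of loss of" at least half of the Week 24 PASI improvement, and "Patients with this ICE will be handled using the composite strategy". Protocol 9.3.3 describes the same event as "ICE 4 (meeting retreatment criterion during the randomized withdrawal period; only applicable to Week 52 endpoints". Neither text names an arm or asks that retreatment has started.

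**Binary endpoints.** SAP 4.3.1.3.1: "Composite strategy will be used for ICEs 1, 2 and/or 4 (as applicable) where participants with those ICEs will be considered as non-responders". Its time-to-event paragraph likewise counts ICE 4 as loss of response. SAP 4.3.2.3 uses the key secondary strategies for the other secondary binary endpoints.

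**Continuous endpoints.** SAP 4.3.2.3 adds a condition that appears nowhere else: "Participants experiencing ICEs 1, 2 and 4 (only apply to Week 52 endpoints after retreatment among adult participants". From that point on, the participant's change from baseline is set to zero.

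**Carry-over.** SAP 4.4.2.2, on the randomized withdrawal period: "Participants experiencing ICEs 1, 2 and/or 4 between Week 24 and Week 52 will be handled in the same manner as the other secondary analyses". SAP 4.4.2.5 then lists change and percent change in PASI from Week 24 through Week 52 for participants randomized at Week 24.

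**Who is retreated.** The footnote on unscheduled visits in protocol 1.3.1 says that a withdrawn participant who has lost at least half is retreated under the blind. For anyone else, "If a participant is not part of the withdrawn treatment group, they will continue on their treatment per study design".

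**The concern.** One intercurrent event has two triggers. For binary and time-to-event endpoints the trigger is a PASI threshold, which a participant in either arm can cross. For continuous endpoints the trigger is being past retreatment, which can happen only in the withdrawal arm.

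Two participants with identical PASI courses would then get different scores. The one on withdrawal is set to zero improvement from that point; the one on continued JNJ-77242113 contributes the measured value. Part of any difference in mean PASI change would come from the imputation rule.

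In SAP 4.4.2.5 the PASI 75/90/100 summaries and the PASI change summaries cover the same participants and visits, yet they would rest on different ICE 4 populations. Two programmers could also read the SAP differently: one following 4.3.1.2.1 would impute in both arms, and one following 4.3.2.3 in one arm only.

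**Working it through.** **1. The rule by endpoint type, read literally**

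| Endpoint type | Trigger | Withdrawal arm | Continued arm |
|---|---|---|---|
| Binary (SAP 4.3.1.3.1, 4.3.2.3) | criterion met | non-responder | non-responder |
| Time to event (SAP 4.3.1.3.1) | criterion met | event | event |
| Continuous (SAP 4.3.2.3) | after retreatment | zero change | observed value |

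The continued-arm entries in the first two rows are inferred from the absence of any arm limit.

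**2. Reach.** All four adult Week 52 other secondary endpoints in SAP Table 6 are binary or time-to-event. The continuous outcome listed for the re-randomized adults is the exploratory PASI change and percent change in SAP 4.4.2.5. Exploratory p-values are nominal (SAP 4.1, 4.4.2).

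**3. The plan's own figures.** Arm size: 540 adults × 2/3 × 0.75 ÷ 2 = 135, as in SAP Table 9. Power for PASI 75 at Week 52 (two-sided 0.05, normal approximation with pooled variance under the null), for 60% versus 80%:

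- null SE = √(2 × 0.70 × 0.30 / 135) = 0.0558
- alternative SE = √((0.60 × 0.40 + 0.80 × 0.20) / 135) = 0.0544
- power = Φ((0.20 − 1.96 × 0.0558) / 0.0544) = 95.2%

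The three rows come to 95.2%, 97.0% and 98.7%, against 95.2%, 97.0% and 98.6% stated. These figures concern a binary endpoint, so the wording at issue does not touch them.

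**4. Size of the shift.** Let *r* be the share of the continued arm meeting the criterion and *I* the mean Week 24 percent improvement. The documents give neither, so both are assumptions. At the visit where the criterion is met, at most half of *I* remains. Relative to a rule that also imputes zero in the continued arm, that arm's mean is raised by

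shift = *r* × residual improvement ≤ *r* × 0.5 × *I*.

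| *I* | Largest residual | *r* = 5% | *r* = 10% |
|---|---|---|---|
| 75% | 37.5 | 1.9 | 3.75 |
| 90% | 45 | 2.25 | 4.5 |
| 100% | 50 | 2.5 | 5.0 |

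The entries are percentage points of PASI improvement, with every relapser exactly at the threshold. The criterion has no floor: the shift falls toward zero as relapsers approach baseline and reverses if they are worse than baseline. It would be larger at later visits for a participant who regains improvement.

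**5. Precision.** With an assumed SD of 25 points, the between-arm SE is 25 × √(2/135) = 3.0 points.

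**6. Plausible range of *r*.** SAP Table 9 plans for 80% to 90% PASI 75 on continued treatment at Week 52. The remaining 10% to 20% must cover ICEs 1 and 2, missing data and every loss of PASI 75, including losses too shallow to meet ICE 4. An *r* of 20% would use up all non-response in the 80% row and twice the non-response in the 90% row. Even 10% would use all of it in the 90% row.

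**The case against.** The strongest reply is that this is loose wording and that ICE 4 has a single definition. SAP 4.3.2.2.2 says the ICEs for adult Week 52 other secondary endpoints are those of the key secondary endpoints. Protocol 9.3.3 calls the event the retreatment criterion. SAP 4.4.2.5 treats time to losing half of the Week 24 improvement as time to retreatment. On that view, the parenthesis only says where ICE 4 applies.

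A second reply is that the literal rule can be defended. Once retreated, a withdrawn participant's scores no longer reflect withdrawal, whereas a continued participant's scores still reflect the assigned treatment.

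Part of this stands. The documents do not show that a one-sided rule was intended, and a one-sided rule could be argued as an estimand choice. The conflict remains, though. The equation in SAP 4.4.2.5 is made for time after withdrawal, where criterion and retreatment coincide; in the continued arm there is no retreatment. SAP 4.3.2.2.2 introduces Table 6, which has no continuous endpoint. If the one-sided rule is deliberate, the SAP neither says so nor explains why it differs from the binary rule for the same visits.

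A reader might also infer that the maintenance claim is biased, or that the shift could reach 5 to 10 points. Neither is supported. The key secondary tests use the criterion-based rule, and the larger shift needs about 20% of the continued arm to meet ICE 4, which the planned response rates make implausible.

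**Conclusion.** The conflict is real and minor. On the literal wording, zero improvement can be imputed for ICE 4 only in the withdrawal arm, and this favours continued JNJ-77242113 for as long as relapsers in the continued arm keep some improvement. It is a conflict to reconcile, not evidence of intent.

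The size depends entirely on assumed values for the relapse share, the residual improvement and the SD. Within the 5% to 10% range, the largest shift is between a little under one and somewhat over one and a half between-arm standard errors (2.5/3.0 and 5/3.0). That could visibly move an exploratory curve or a nominal p-value, but no confirmatory conclusion depends on it. That the definition covers both arms is itself an inference from silence, so the SAP should state it.

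**What to change.** Make two edits.

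- In SAP 4.3.2.3, replace the parenthesis with wording to this effect: *ICE 4 applies to adults re-randomized at Week 24, in either arm, from the visit at which the criterion in Section 4.3.1.2.1 is met.*
- In SAP 4.3.1.2.1, add that the ICE 4 definition applies to both re-randomized arms.

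If the one-sided rule is wanted for continuous endpoints, state it as a separate estimand with its reason.

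No new data are needed: PASI is scheduled at every visit from Week 24 to Week 52 in both arms, so the criterion can be derived for everyone. The downside is that the continuous treatment difference becomes slightly smaller, provided that relapsers in the continued arm retain some improvement.
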